Jan 12, 2010	Immune Function in MS	[name]
NCT03344094		

Study Design/Rationale:

Multiple sclerosis is an inflammatory disease that causes demyelination of the brain and spinal cord. In MS, 20-60 year-old patients, women more than men, develop episodes of neurologic dysfunction that last days to weeks and then partially resolve. Damage is cumulative and eventually becomes progressive. The immune system also evolves over time and becomes less sensitive to immune suppression. Demyelinating variants of MS such as neuromyelitis optica and CNS Sjogren's disease, have similar, but often more severe symptoms.

We will be studying proteins and RNA in white blood cells, and how these change during therapy of MS and demyelinating variants. White blood cells control some immune responses and may control the attacks, progression, and severity of MS. We will also analyze DNA polymorphisms of relevant genes identified in these studies. By studying these white blood cells, we hope to determine what causes MS and use this knowledge to design potential therapies for MS patients in the future.

More specifically, assays will evaluate the following:

Immune function: We will study immune function in multiple sclerosis, with assays of expression of costimulatory molecules and interferon receptors on the cell surface, also cytokine secretion, intracellular cytokines and signal transduction proteins, expression of mRNA for these proteins, NK function, and lymphocyte proliferation. This information is intended to determine the mechanism of action of various therapeutic agents in MS (unknown at this time).

Some examples of the cytokines to be investigated include interleukins, monokines, neuropeptides, interferons, TGF, and TNF; signal transduction molecules include JAK/STAT proteins, NF-kB, kinases, and phosphatases; costimulatory molecules include HLA-DR, B7.1, and B7.2.

The particular assay is dependent on the mechanism of action of the agent being studied in MS. All are variations on the same limited theme; all require a modest amount of blood; and all are subject to the same confidentiality arrangements. As examples, we will use ELISA and RT-PCR to measure lymphocyte production of cytokines (such as IL-10 and IFN-gamma) protein and mRNA because of its relevance to immune function in MS patients before and after interferon therapy; use flow cytometry to measure lymphocyte B7.1 membrane expression for comparison to patients receiving Copaxone therapy, use Western blots and intracellular flow cytometry to measure STAT-1 levels for comparison to patients receiving interferon therapy, and use RT-PCR, micro arrays and next generation RNA sequencing to measure RNA levels and exon use.

Assays are done on blood from clinic population of MS patients and healthy agematched normal controls, and from clinical trial patients. Blood from patients who are not part of trials, and also from patients who are in trials--before and after drug therapy, will be analyzed during the course of the study and compared to untreated patients and controls Clinic visits typically occur at 3-12 month intervals. Trials of experimental or FDA-approved drugs last 1-3 years and typically require visits every 2-6 months. Blood will be drawn at regular clinic visits before therapy, at 1 & 3 mo, and at 1, 2, and 3 years after starting treatment, depending on duration of study. Research will take place in J218 and J220, SBRP.

Kinetics: Some patients with stable and active and progressive MS will be tested while on drug treatment. Here we will measure kinetic effects of immunomodulatory drugs. In the latter patients, blood will be drawn before, and at 4, 18, and 42 hours or 5 days after drug administration.

DNA: Blood from some patients with each form of MS and family members will be analyzed for genes linked to MS and controlling immune function. In some cases, DNA may be obtained from buccal scraping or other body fluids. Multiple sclerosis is caused by interactions of multiple genes. This is a broad screen of multiple genes to determine linkage to MS, and to determine responses to interferons. Separate data on immune function, also without identifiers, will be compared to genes of interest. These genes include, but aren't limited to, those regulating all aspects of immunity, cell survival, matrix metalloproteases and migration, kinases and phosphatases, and cell cycling, and pH regulation.

In addition, we will assay methylation of DNA (circulating in plasma). Some genes are methylated, a marker of their ability to be turned on that reflects cell regulation and death. When cells die, they release DNA. Sensitive assays can detect methylated forms of DNA from relevant genes (*i.e.*, methylation-sensitive restriction enzyme digestion, then PCR).

Al of these assays are directed at finding the immunologic cause of MS, how to predict exacerbations, and how to optimize MS therapy.

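### Healthy controls are matched to MS patients on age only, so comparisons of patients with healthy controls are open to confounding by sex

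*Combined protocol and SAP*

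**What the plan says.** The combined protocol and SAP addresses this point in four places.

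- **Control selection** (sample-source paragraph under Immune function, before Kinetics): "Assays are done on blood from clinic population of MS patients and healthy agematched normal controls". Age is the only factor named.
- **Patient population** (Study Design/Rationale): "In MS, 20-60 year-old patients, women more than men, develop episodes of neurologic dysfunction". No ratio is given, and this is the only mention of sex in the document.
- **Planned comparison** (same paragraph as control selection): patient samples "will be analyzed during the course of the study and compared to untreated patients and controls". No model, test or covariate is given for this comparison.
- **Aim** (last sentence of the DNA section): all "of these assays are directed at finding the immunologic cause of MS", together with predicting exacerbations and optimising therapy.

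The plan also has comparisons within the same patient. Samples are taken serially ("Blood will be drawn at regular clinic visits before therapy", then at intervals after treatment starts), and the Kinetics section compares samples before and after a drug dose.

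**The concern.** By matching on age, the protocol accepts that controls must resemble patients demographically. It leaves out the other demographic factor that its own rationale ties to the disease. Age matching does not control the sex mix: two groups can have identical age distributions and different shares of women.

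If the shares differ, any cytokine, costimulatory molecule, signalling protein or RNA level that differs between men and women will also differ between patients and healthy controls, and the difference could be read as an effect of MS. Before-and-after data show what treatment does. They do not show how MS patients differ from healthy people, so the aim of finding an immunologic cause leans on the comparison at risk. The bias does not shrink with sample size; a larger study only makes the false difference more likely to reach significance. The assay panel is broad (microarrays and RNA sequencing are included), so not every marker needs to differ by sex for some false leads to arise.

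**Working it through.** **Reading check.** The whole document was read for matching, stratification, restriction or adjustment by sex. There is none. There is also no planned figure to reproduce: no sample size, effect size, SD, significance level or sex ratio is stated. The numbers below are therefore an illustration on assumed inputs.

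**Assumed inputs (none from the document).** Women are 60–75% of patients and 50% of controls, with a 60% control share as a milder case. The sex difference in a marker is 0.2–0.8 SD. There are 30–200 donors per group, no true MS effect, and a two-sided 5% z-test without adjustment.

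**Formulas.**

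- Bias = (share of women in patients − share of women in controls) × sex difference.
- SE = √(2/n), with total SD = 1.
- False-positive rate = 1 − Φ(1.96 − bias/SE) + Φ(−1.96 − bias/SE).

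**Worked case.** 70% versus 50%, 0.5 SD, n = 100 per group:

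- Bias = 0.20 × 0.5 = 0.10 SD.
- SE = √(2/100) = 0.141, so bias/SE = 0.707.
- Rate = 1 − Φ(1.253) + Φ(−2.667) = 0.105 + 0.004 = 0.109.

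**Range.**

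| Women, patients vs controls | Sex difference (SD) | Bias (SD) | n=30 | n=50 | n=100 | n=200 |
|---|---|---|---|---|---|---|
| equal | any | 0 | 5.0% | 5.0% | 5.0% | 5.0% |
| 60% vs 50% | 0.2 | 0.02 | 5.1% | 5.1% | 5.2% | 5.5% |
| 70% vs 60% | 0.5 | 0.05 | 5.4% | 5.7% | 6.4% | 7.9% |
| 60% vs 50% | 0.8 | 0.08 | 6.1% | 6.9% | 8.7% | 12.6% |
| 70% vs 50% | 0.5 | 0.10 | 6.7% | 7.9% | 10.9% | 17.0% |
| 75% vs 50% | 0.8 | 0.20 | 12.1% | 17.0% | 29.3% | 51.6% |

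If the sex difference is measured in within-sex SDs instead, the variance of each group rises slightly and the last row becomes 11.2%, 15.5%, 26.3% and 46.6%. If controls had the larger share of women, the bias would have the opposite sign and the rates would be the same.

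**Does adjustment work?** Simulation with 4,000 runs per case, within-sex SD = 1 and no MS effect:

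| Case | Rate without sex covariate | Rate with sex covariate |
|---|---|---|
| 70% vs 50%, 0.5 SD, n=100 | 10.2% | 5.1% |
| 75% vs 50%, 0.5 SD, n=100 | 14.7% | 5.0% |
| 75% vs 50%, 0.8 SD, n=200 | 46.0% | 4.5% |
| equal shares, 0.5 SD, n=100 | 5.0% | 4.7% |

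**What adjustment costs.** The SE is multiplied by √(1/(1 − ρ²)), where ρ is the correlation of group with sex. For equal groups, ρ² = 0.25 × (difference in shares)² / [p(1 − p)], with p the pooled share of women. For 75% versus 50%, p = 0.625 and ρ² = 0.25 × 0.0625 / 0.2344 = 0.067, giving a factor of 1.035. For 70% versus 50%, ρ² = 0.042 and the factor is 1.022. For 60% versus 50%, ρ² = 0.010 and the factor is 1.005.

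**The case against.** The strongest reply has four parts.

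1. **The comparison is not the main one.** The Immune function text says these assays are meant to show how treatments act, and its examples centre on treatment, such as "immune function in MS patients before and after interferon therapy". Serial and kinetic samples hold sex fixed. This is correct and limits the reach of the point. The healthy-control comparison is nevertheless planned in so many words.
2. **The harm is not demonstrated.** It needs a sex imbalance and markers that differ by sex, and the document establishes neither. The remark about women is a general description of MS, not a count of this clinic's patients. This stands: the omission is certain, the bias is not. A design review, however, asks whether the written rule prevents a foreseeable problem, and this one does not.
3. **The figures follow from the inputs chosen.** Nothing supports 200 per group, and with 70% versus 60% women and a 0.5 SD difference the rate is only 5.4% to 7.9%. This also stands, and the 52% should not be quoted as a typical value.
4. **This is a short exploratory plan that gives no analysis detail for any comparison.** That is true, but the point is more than missing detail. A matching rule is stated, and it can be followed to the letter while leaving the confounding in place.

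A further remark widens the point. Comparisons of treated with untreated patients are also between groups and could differ in sex mix.

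**Conclusion.** The concern holds. Age is the only matching factor named, no handling of sex is stated, and the protocol itself says the disease is commoner in women, so comparisons of patients with healthy controls are exposed to confounding by sex.

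The size cannot be determined from the document. It is zero if the sex mix is equal or the marker does not differ by sex, and negligible at the low end of the assumed range (5.1% to 5.5%). In the middle case at 100 per group it is 0.10 SD, or about 11% false positives. It reaches about 52% (47% on within-sex SDs) only when all three inputs take their largest assumed values together. Comparisons within the same patient are not affected. The study is not invalidated, but this is a foreseeable bias with a cheap remedy and should be corrected.

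**What to change.** - In the sample-source paragraph, require healthy controls to be matched on age and sex. Frequency matching of the sex mix within age bands is enough; individual pairing is not needed.
- Record sex for every donor and include it as a covariate in every comparison of patients with healthy controls. Doing the same for treated versus untreated patients is a natural extension.
- If controls have already been collected, adjust for sex and report the sex mix of each group.

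The cost is slightly more effort in choosing control donors and one recorded variable per donor. If sex is adjusted for but not matched, the standard error of the comparison grows by about 0.5% (60% versus 50% women) to 3.5% (75% versus 50%). With frequency matching that loss is nil.

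### Samples drawn up to 3 years apart are assayed as the study proceeds, and nothing in the plan keeps assay run apart from time on treatment, so drift can pass for a drug effect

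*Combined protocol and SAP*

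**What the plan says.** All of this is in the combined protocol and SAP, under Study Design/Rationale, mostly in the Immune function text.

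- **Timing of assay.** On blood from patients in trials: "before and after drug therapy, will be analyzed during the course of the study and compared to untreated patients and controls".
- **Timing of draws.** "Blood will be drawn at regular clinic visits before therapy, at 1 & 3 mo, and at 1, 2, and 3 years after starting treatment". The later draws apply only as far as the length of the study allows. Visit spacing in the parent trials is described as follows: "Trials of experimental or FDA-approved drugs last 1-3 years and typically require visits every 2-6 months".
- **Comparators.** "Assays are done on blood from clinic population of MS patients and healthy agematched normal controls, and from clinical trial patients". No repeat-draw schedule specific to the untreated or healthy groups is given, and no rule says that they share runs with treated samples.
- **Readouts.** For the interferon before/after example, "we will use ELISA and RT-PCR to measure lymphocyte production of cytokines". More broadly, the laboratory will "use RT-PCR, micro arrays and next generation RNA sequencing to measure RNA levels and exon use". Flow cytometry, Western blots, NK function and lymphocyte proliferation are also named.
- **Purpose.** "This information is intended to determine the mechanism of action of various therapeutic agents in MS".

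The documents do not mention storing a patient's series for a single run, reference or bridging samples, run order, or a run term in the analysis.

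**The concern.** Within a patient the pre-treatment sample always comes first, and the last on-treatment sample may follow 3 years later. If each is assayed near the time it is drawn, reagent lots, array batches and sequencing runs change in the same direction as time on treatment. A before/after difference then contains the drug effect plus whatever the assay did in between.

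The study intends to read such changes as evidence of how a drug acts, so a shift in the assay could be reported as a mechanism. Adding patients does not help when they share the same runs: the standard error shrinks while the run difference stays.

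**Working it through.** **Inputs from the documents.** The longest gap between the pre-treatment and on-treatment draw is 3 years. Analysis is ongoing. There is no stated sample size, test, significance level, SD or assay precision, so there is no planned figure to reproduce.

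**Assumed inputs.** A paired t-test at two-sided 5%; no true drug effect; n = 20 or 40; within-person SD of 1 per measurement; independent run effects with SD s = 0.25, 0.5 or 1.0.

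**Step 1: worst layout, all pre-treatment samples in one run and all on-treatment samples in another.** The mean difference has variance 2/n + 2s² = (2/n)(1 + n·s²). The run difference is the same for every patient, so it does not enter the estimated SD. The t statistic is therefore inflated by k = √(1 + n·s²), and the false-positive rate is P(|T| > t_crit/k) on n − 1 df. The critical value is 2.093 for n = 20 and 2.023 for n = 40.

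| n | s | k | t_crit/k | rate |
|---|---|---|---|---|
| 20 | 0.25 | √2.25 = 1.50 | 1.395 | 0.179 |
| 20 | 0.5 | √6 = 2.45 | 0.855 | 0.403 |
| 20 | 1.0 | √21 = 4.58 | 0.457 | 0.653 |
| 40 | 0.25 | √3.5 = 1.87 | 1.081 | 0.286 |
| 40 | 0.5 | √11 = 3.32 | 0.610 | 0.545 |
| 40 | 1.0 | √41 = 6.40 | 0.316 | 0.754 |

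Simulation of the same layout agrees: 0.18, 0.39, 0.65, 0.29, 0.54, 0.75.

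**Step 2: less extreme layouts (simulated, same n and s).**

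| Layout | Range of rates |
|---|---|
| Four runs each side, none shared | 8% to 44% |
| Quarterly runs, 3-year gap, entry over 8 quarters | about 6% to 29% (repeat simulations put the top end at 29% to 31%) |
| Quarterly runs, 3-year gap, entry over 20 quarters | about 5% to 12% |
| Each patient's samples in the same run | about 5% (0.047 to 0.051 for n = 10, 20, 40) |

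Staggered entry averages random run shifts over more runs, so the excess falls but does not vanish in most settings.

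**Step 3: steady drift.** Calendar time is entry date plus time on treatment. A constant drift rate over a fixed gap therefore adds the same amount to every patient's change, whatever the entry date, and staggering dilutes nothing. With drift D over the gap, now in SDs of the within-patient change (a different scale from s), the rate is Φ(D√n − 1.96) + Φ(−D√n − 1.96). For n = 20 and D = 0.25, D√n = 1.118, giving Φ(−0.842) + Φ(−3.078) = 0.20.

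| n | D = 0.1 | D = 0.25 | D = 0.5 |
|---|---|---|---|
| 10 | 0.06 | 0.12 | 0.35 |
| 20 | 0.07 | 0.20 | 0.61 |
| 40 | 0.10 | 0.35 | 0.89 |

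**Step 4: comparators.** Subtracting the change in untreated patients cancels drift common to both groups, provided that they are drawn again over the same interval and assayed in the same runs. A single draw per comparator gives no change to subtract.

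**The case against.** Several parts of the opposing case are sound and limit the point.

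- **The text does not prescribe assay at each visit.** A laboratory that stored each series and ran it together could still say it analyzed blood during the study. A reader might infer that batching is excluded; it is not. The plan is silent, and only fresh-cell work is forced into separate runs.
- **Run and treatment time need not coincide for every patient.** A reader might infer complete alignment. No common start date is given, and with staggered entry one patient's pre-treatment sample can share a run with another's on-treatment sample. Random shifts are then partly separable; steady drift is not.
- **Comparators are planned.** It would be wrong to say the change is judged with no reference group. What is missing is serial sampling of that group in shared runs.
- **The before/after contrast is not declared primary.** No primary outcome is named, and the study also aims at cause, prediction of exacerbations and optimizing therapy. Of the assay examples, only the ELISA and RT-PCR one is explicitly before and after treatment; the B7.1 and STAT-1 examples are comparisons with patients receiving therapy.
- **Holding samples has its own confounder.** Pre-treatment material would be stored up to 3 years longer than the last sample. This stands, and the fix must deal with it.

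None of this supplies the missing safeguard: no statement in the plan separates run from time on treatment.

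**Conclusion.** The concern holds as a gap in design. As written, the multi-year before/after change is open to assay drift. This is unavoidable for fresh-cell assays without concurrent references, and it applies to storable material unless the laboratory batches it.

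The size is unknown, because every quantity that sets it (number of patients, run SD, drift, entry pattern, test) is assumed here. The 18% to 75% range is a worst case and should not be read as the study's expected error rate, since the documents do not describe a layout of one run per side. Under the same assumptions, staggered entry gives about 6% to 29% or about 5% to 12%. The 5% benchmark is itself an assumption, as the plan sets no significance level.

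The point does not apply to the Kinetics draws (4, 18 and 42 hours or 5 days) or to DNA polymorphisms. It applies to plasma DNA methylation only if that is compared before and after therapy, which the DNA section does not say. It merits action because material already assayed and used up cannot be re-run.

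**What to change.** State in the plan how assay runs are arranged.

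1. **Storable material with a before/after contrast** (RNA, culture supernatants, and lysates where compared serially). Assay all of a patient's time points in the same plate, array batch or sequencing run. Include in each run serial samples from untreated patients stored over a similar gap, and compare the treated change with the untreated change, so that storage time does not replace run as the confounder.
2. **Fresh-cell assays** (flow cytometry, NK function, proliferation). Schedule an already planned untreated or healthy control on the same day, express treated values relative to it, and fit run as a random effect. The run term is useful only because each run then contains a reference; without one it cannot remove steady drift.
3. If the laboratory already batches stored series, one sentence saying so, with the storage-matched untreated samples added, closes the point for that material.

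**Cost.** Freezer space, later availability of some serial results, and timing (possibly repeating) the control draws to match fresh-assay days. No additional treated patients and no extra blood from them are needed.

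### The long-term on-treatment draws neither fix nor record time since last dose, so post-dose phase may dilute, and could confound, comparisons of dose-responsive markers

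*Combined protocol and SAP*

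**What the plan says.** Under Study Design/Rationale, the Immune function part sets the long-term schedule: "Blood will be drawn at regular clinic visits before therapy, at 1 & 3 mo, and at 1, 2, and 3 years after starting treatment". The visits themselves are spaced in months. For clinic patients, "Clinic visits typically occur at 3-12 month intervals"; for trial patients, "Trials of experimental or FDA-approved drugs last 1-3 years and typically require visits every 2-6 months". The only clock for these draws is time since treatment began. No sentence in the document sets a window relative to the last dose, asks for the time of that dose, or adjusts for it.

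These samples feed the main comparisons. Blood taken "before and after drug therapy, will be analyzed during the course of the study and compared to untreated patients and controls". The assays include some that could respond to a recent dose; for example, the investigators will "use Western blots and intracellular flow cytometry to measure STAT-1 levels for comparison to patients receiving interferon therapy".

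The Kinetics paragraph, which follows directly, uses a different clock. "Some patients with stable and active and progressive MS will be tested while on drug treatment", and for the dose-timed group "blood will be drawn before, and at 4, 18, and 42 hours or 5 days after drug administration". Its purpose is given in one sentence: "Here we will measure kinetic effects of immunomodulatory drugs". The plan does not say how the kinetic results will inform the timing or reading of the long-term draws.

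**The concern.** Two samples both labelled 3 months may have been taken at quite different times after a dose, and the data would not show it. The same holds for one patient's 3-month and 1-year samples. If a marker rises after a dose and then falls back before the next one, its long-term value mixes a transient response with any sustained change.

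The plan wants to learn how the agents act and how to improve their use. Both aims depend on telling a short-lived post-dose response from a lasting shift in immune function. If the last-dose time is not written down at the draw, it is hard to recover later, and no analysis can then separate the two.

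**Working it through.** **No stated figure to reproduce.** The document gives no sample size, effect size, standard deviation, dosing interval or marker half-life. The main check is therefore a reading of the text; the arithmetic below is illustration only.

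**Reading the schedules side by side.**

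| | Long-term draws | Kinetic series |
|---|---|---|
| Who | Treated clinic and trial patients | Some patients on drug |
| Clock | Start of treatment, at visits | A given dose |
| Times | Before; 1 and 3 months; 1, 2 and 3 years | Before; 4, 18 and 42 hours or 5 days |
| Time since last dose | Not fixed, not recorded | Fixed by design |

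Visits set months apart do not by themselves determine hours since dose.

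**Illustration: assumptions.** After a dose, the transient effect decays as f(t) = exp(−kt), with k = ln 2 / h for half-life h and peak set to 1. Draw time is uniform over the dosing interval τ. Both h and τ are assumed. The values of h (18, 42 and 120 hours) match times in the kinetic series for convenience; they are not estimates.

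With x = kτ:
- mean effect m = (1 − e^(−x)) / x
- second moment m₂ = (1 − e^(−2x)) / (2x)
- phase SD = √(m₂ − m²)

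Worked case, τ = 48 and h = 18: x = 48 × 0.6931 / 18 = 1.848; m = (1 − 0.1575) / 1.848 = 0.456; m₂ = (1 − 0.0248) / 3.697 = 0.264; phase SD = √(0.264 − 0.208) = 0.24.

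| τ (h) | h (h) | Mean / peak | Phase SD / peak |
|---|---|---|---|
| 48 | 18 | 0.46 | 0.24 |
| 48 | 42 | 0.69 | 0.16 |
| 48 | 120 | 0.87 | 0.07 |
| 168 | 18 | 0.15 | 0.23 |
| 168 | 42 | 0.34 | 0.26 |
| 168 | 120 | 0.64 | 0.18 |

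**Dilution or noise?** Assume a peak effect of 1 between-patient SD, two-sided alpha 0.05 and power 0.80. Then n per group = 2(1.96 + 0.8416)² × s² / δ² = 15.70 × s² / δ², where s² = 1 + v/2 averages the two groups' variances and v is the phase variance. For τ = 48 and h = 18:
- all draws at 4 hours: δ = 0.857, s² = 1, n = 15.70 / 0.735 = 21.4, so 22
- random phase: δ = 0.456, s² = 1.028, n = 15.70 × 1.028 / 0.208 = 77.7, so 78
- random phase with the added variance ignored: n = 76

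Of the rise from 22 to 78, only 2 per group comes from extra variance. The rest is the smaller average effect. The 4-hour draw is a favourable reference, not a proposal.

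**If phase differs systematically.** Take the extreme in which every draw at one visit falls at 4 hours and every draw at another at 42 hours, with the drug effect unchanged. The apparent fall, f(4) − f(42), is 0.857 − 0.198 = 0.66 of peak for h = 18, 0.936 − 0.500 = 0.44 for h = 42, and 0.977 − 0.785 = 0.19 for h = 120. Similarly, two agents with the same peak and h = 42, one at τ = 48 and the other at τ = 168, would show mean effects of 0.69 and 0.34 of peak at random phase.

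**The case against.** The strongest objection is that the plan never says markers move within hours. It says that kinetic effects will be measured, with no direction, size or time course. That is correct. A reader might infer from the 4-, 18- and 42-hour draws that the plan expects rapid movement; the text supports only the weaker inference that post-dose time may matter.

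A reader might also infer that phase contaminates every treated-versus-untreated and before-versus-after comparison. The document does not support this. The kinetic comparisons are themselves dose-timed, inherited polymorphisms do not change with dose, and comparisons of untreated patients with controls involve no dose. Sustained effects, or steady drug exposure, would be little affected.

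Third, if phase is random, the expected group means at 3 months and 1 year are equal when the drug effect is unchanged. Phase then dilutes the effect and adds some noise; it does not create a group trend. A false trend needs phase to differ systematically between visits, and the document gives no evidence that it does. Nor does it spell out a formal comparison between agents, where unequal dosing intervals would matter most. This stands, and it is why confounding is stated conditionally.

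Finally, one might ask for all draws at a single phase per agent, such as just before a dose. That has a price. In the model with τ = 168 and h = 42, a pre-dose sample shows e^(−2.77) = 0.06 of peak, against 0.34 at random phase. It isolates sustained change but loses most of the transient signal. It would also have to fit the visit schedules of the trials that patients are in.

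None of this answers the central gap: time since last dose is neither controlled nor recorded.

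**Conclusion.** The concern holds in a limited form. The long-term on-treatment draws leave post-dose phase unknown, while the adjacent kinetic series treats it as worth measuring. For dose-responsive markers in intermittently dosed patients, this may dilute before-versus-after and treated-versus-untreated comparisons. It may bias comparisons between visits or agents only if phase differs systematically between them.

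The size is not knowable from the document. The illustrative range, from slight dilution (0.87 of peak) to near loss of the transient effect (0.15), rests wholly on exponential decay, uniform phase, and assumed half-lives and intervals. The problem is small when the effect outlasts the dosing interval and large when it is short relative to it. The firmer argument is interpretability: without the dose time, transient and sustained effects cannot be told apart afterwards. The change should be made.

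**What to change.** 1. At every on-treatment draw, record the date and time of the last dose. Leave dosing and visits unchanged, and keep every sample.
2. Use the plan's kinetic series to identify which markers vary with time since dose.
3. For those markers, adjust for or stratify by hours since last dose in the long-term comparisons, and state this in the plan before those analyses.

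The cost is one extra item on the draw form and a small amount of added analysis. No extra blood, patients or assays are needed. Recording the time does not restore signal lost by sampling late after a dose; it lets that loss be recognised and modelled. Fixing a single draw phase per agent is optional, given the trade-off described above, and is not part of the required change.

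### Can the hour-scale kinetic samples be read as drug effect when they fall at different times of day?

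*Combined protocol and SAP*

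**What the plan says.** The Kinetics paragraph of Study Design/Rationale describes a substudy within treated patients: "Some patients with stable and active and progressive MS will be tested while on drug treatment". Its purpose is one sentence: "Here we will measure kinetic effects of immunomodulatory drugs". The schedule is that "blood will be drawn before, and at 4, 18, and 42 hours or 5 days after drug administration".

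The paragraph gives no clock time for the dose or for any draw, no interval between the pre-dose sample and the dose, and no sampling window. It gives no number of patients, test or significance level.

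The preceding paragraph describes draws on a much longer scale ("Blood will be drawn at regular clinic visits before therapy, at 1 & 3 mo, and at 1, 2, and 3 years") and says that blood samples "will be analyzed during the course of the study and compared to untreated patients and controls". No hour-scale series in undosed people is described. The assays are broad: "assays of expression of costimulatory molecules and interferon receptors on the cell surface, also cytokine secretion, intracellular cytokines and signal transduction proteins", together with mRNA, NK function and lymphocyte proliferation. Nothing is said about daily variation in any of them.

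**The concern.** Eighteen and 42 hours are not whole days. Samples at those times are taken at a different time of day from the dose, and so is the 4-hour sample. If a marker rises and falls over the day, its change from the pre-dose sample mixes the drug effect with the clock.

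The pattern would be misleading in a particular way. A marker that ignores the drug but follows the clock would shift by the same amount at 18 and 42 hours and return at 5 days. That looks like a sustained response followed by recovery. If 5 days is an alternative to the hourly samples, it would look instead like a difference between two sets of patients. The comparison with untreated patients and controls does not remove this as described, because their draws are tied to clinic visits. At stake is the reading of mechanism and time course, which is what this substudy is for.

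**Working it through.** **Inputs.** From the Kinetics paragraph: sample times 4, 18 and 42 hours and 5 days. Assumed: the pre-dose sample (pre) is at 0 h and 5 days means 120 h. The plan states no figure of its own to reproduce.

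**Clock offsets.** For two samples d hours apart, let r be the remainder of d divided by 24. The offset is the smaller of r and 24 − r.

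| Pair | d (h) | Offset (h) |
|---|---|---|
| pre v 4 h | 4 | 4 |
| pre v 18 h | 18 | 6 |
| pre v 42 h | 42 | 6 |
| pre v 5 d | 120 | 0 |
| 4 v 18 h | 14 | 10 |
| 4 v 42 h | 38 | 10 |
| 4 h v 5 d | 116 | 4 |
| 18 v 42 h | 24 | 0 |
| 18 h v 5 d | 102 | 6 |
| 42 h v 5 d | 78 | 6 |

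Two of the ten pairs are matched.

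**Size of a false change.** Assume a 24-hour cosine with peak-to-trough P. The largest false difference at offset L is P × sin(πL/24), and its average over all phases is that times 2/π.

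- L = 4: 0.50P, average 0.32P.
- L = 6: 0.71P, average 0.45P.
- L = 10: 0.97P, average 0.61P.
- L = 0: none.

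Dosing midway up the rhythm, with no drug effect, gives +0.43P, −0.50P, −0.50P and 0 at 4 h, 18 h, 42 h and 5 days.

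**False-positive rates.** These need further assumptions, none of them in the documents: 20 patients, a paired t-test at two-sided 5%, and P as a multiple of the SD of the paired difference. The shift at 18 or 42 h is 0.707P. The rate comes from the noncentral t with 19 degrees of freedom and noncentrality (shift/SD) × √20.

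| P (SD) | Worst phase | Averaged over phases | Worst phase, dosing spread over 8 h |
|---|---|---|---|
| 0.25 | 12% | 8% | 10% |
| 0.5 | 32% | 19% | 24% |
| 1.0 | 85% | 50% | 70% |

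The last column multiplies the shift by sin(8π/24)/(8π/24) = 0.83. At the most favourable phase, or with P = 0, the rate is 5%. At P = 0.5 SD and the worst phase, 10, 20 or 40 patients give 17%, 32% or 59%.

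**Sensitivity to the assumed times.** Offsets from the pre-dose sample to 4 h, 18 h, 42 h and 5 days:

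- taken at dosing: 4, 6, 6, 0;
- 2 h earlier: 6, 4, 4, 2;
- 6 h earlier: 10, 0, 0, 6.

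A 5-day draw that is 4 h early or late has an offset of 4 h even with the pre-dose sample at dosing. Only 18 v 42 h stays matched whatever the pre-dose time.

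**Would moving the pre-dose sample help?** Taking it 6 h earlier raises the worst case from 0.50P to 0.97P at 4 h and from 0 to 0.71P at 5 days. It lowers the worst case from 0.71P to 0 at both 18 and 42 h. The four worst cases sum to 0.500 + 0.707 + 0.707 + 0 = 1.91P at dosing time and 0.966 + 0 + 0 + 0.707 = 1.67P when moved. No pre-dose time matches every sample.

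**The case for a change.** The best case for acting is that the remedy looks almost free. Writing down the clock time of each draw and of the latest dose needs no blood, and times that are not recorded may be lost for good. Relaxing the assumption about the pre-dose sample does not rescue the schedule, since some contrasts are unmatched wherever it falls. The false pattern also resembles a genuine response.

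Much of that stands. The offsets are exact under their condition, the documents describe no undosed hour-scale series, and noting both times is good practice. But a recorded time alters no estimate by itself, and it allows adjustment only if dosing times differ between patients.

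The steps that would alter a conclusion fare worse. Resting the kinetics on 18 v 42 h and pre-dose v 5 days sets aside every contrast that addresses onset, and the second pair is matched only under two unstated conditions. If doses were given every 24 hours (an assumption), those pairs would compare equal times since the last dose: 18 h with 18 h, and 24 h with 24 h. They would then say little about kinetics. An undosed series would separate the two effects, but it adds up to five draws per control and assumes the same rhythm in both groups. With equal group sizes and SDs it widens the standard error by √2 = 1.41. Describing the pre-dose sample as an on-treatment level only repeats what the paragraph already says.

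**Conclusion.** The observation is correct and conditional; it does not call for a change. With the pre-dose sample at dosing time and 5 days taken as 120 hours, eight of the ten pairs differ in clock time, by 4 to 10 hours. If a marker follows a cosine daily rhythm, a change from the pre-dose sample could be wrong by at most 0.50P at 4 hours and 0.71P at 18 or 42 hours.

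The documents give no evidence about P for any assay. The bias may therefore be nil, and the error rates are illustrations and not properties of this study. What is absent is operational detail that a laboratory running timed draws would normally record. Each alternative that could change a result either gives up kinetic information or needs more blood, and both are defensible trade-offs. When results are reported, the clock-unmatched contrasts should be read with time of day as a possible contributor; all the planned contrasts can stay.
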